# 11.3.5 Cohort for Secondary Endpoint

The Secondary Endpoint, Change in WOMAC Pain, will be made using the Per-Protocol Cohort. Analyses for all other secondary endpoints will be repeated using the Safety/ITT Cohort and the Per-Protocol Cohort

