## 11.2.2 Secondary Effectiveness Endpoints

One of the secondary objectives of the study is to show that 6-weeks after treatment the Active Treatment group has a similar amount of pain relief as the Sham Treatment group. Change in WOMAC Pain from the Baseline visit to the six-week visit will be calculated for each subject as:

Change in WOMAC Pain =

6-Week Visit WOMAC Pain – Baseline Visit WOMAC Pain

such that a negative value indicates a decrease in the WOMAC Pain, while a positive value indicates the opposite.

The difference in the average Change in WOMAC Pain between the two treatment groups will be calculated as Active Change in WOMAC Pain average - Sham Change in WOMAC Pain average, such that a positive difference indicates that the Active Treatment Group had a larger average Change in WOMAC Pain than the Sham Treatment group, while a negative value indicates the opposite. Since a negative Change in WOMAC Pain is indicative of pain relief, then a negative difference between treatment groups reflects a positive outcome for the study.

A non-inferiority hypothesis test using the two-independent sample t-test will be used to statistically evaluate the difference in the mean Change in WOMAC Pain between the two treatment groups. A confidence interval for the difference in the average Change in WOMAC Pain between the two treatment groups will be provided to assist in the interpretation of the results.

The objective of this secondary endpoint is to show that the average reduction in WOMAC Pain for the Active Treatment group is not worse than the average reduction for the Sham Treatment group by more than one-half of the common standard deviation for the Change in WOMAC Pain scores. The objective is met when the resulting t-test is statistically significant using a one-sided  $\alpha = 0.025$  level of statistical significance.

A variety of additional secondary effectiveness endpoints will be assessed to further characterize pain relief, functional performance, and range of motion. These include:

- Active Range of Motion
- 40 Meter Walk Test
- 30 Second Chair Test
- Length of Hospital Stay
- WOMAC Scores (Pain, Stiffness, and Function)
- SF-36 Scales and Summary Measures
- PROMIS-29 Profile Domains and Pain Intensity Score
- NRS for Pain

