# 11.3.2 Safety/ITT (Intent to Treat) Cohort

All subjects who are randomized are included in the Safety/ITT Cohort. Subjects are analyzed in the treatment group they are randomized to.

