## 11.3.3 Per-Protocol Cohort

The Per-Protocol Cohort is defined as the group of subjects who are randomized in the study, who receive the treatment they are randomly assigned to receive, and who complete their 6-week visit without any major protocol deviations.

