# 11.3.4 Cohort for Primary Endpoint

The objective for the primary Effectiveness endpoint needs to be met for the study to be a The analysis of the primary Effectiveness endpoint, Total Daily Morphine Equivalent, will be made using the Per-Protocol Cohort.

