#### 11.5 **Handling of Dropouts or Missing Data**

All endpoints will be analyzed "as-is" without any special data imputation methods used to replace missing data. Consequently, subjects missing results for a specific analysis will be excluded from that analyses.

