# 11.9 Sensitivity Analyses

No imputations for missing data will be made for the Primary and Secondary Effectiveness Endpoints. All patients enrolled and randomized in the study will be included in all analyses. Sensitivity analyses may be considered and will be described in the final Statistical Analysis Plan for the study. Nevertheless, the totality of the results will be used when evaluating overall Study Success.

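### The WOMAC Pain non-inferiority objective is decided in the Per-Protocol Cohort alone, unlike every other secondary endpoint and at odds with Section 11.9

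*Protocol*

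**What the plan says.** - **The test.** Section 11.2.2 on change in WOMAC Pain at week 6: "A non-inferiority hypothesis test using the two-independent sample t-test will be used". Its objective is met if the test is significant at one-sided 0.025. Section 11.10 sets the margin at 11 points, about half of the assumed standard deviation of 22.
- **The cohort for that test.** Section 11.3.5: "The Secondary Endpoint, Change in WOMAC Pain, will be made using the Per-Protocol Cohort".
- **The cohorts for the rest.** The next sentence of 11.3.5: "Analyses for all other secondary endpoints will be repeated using the Safety/ITT Cohort and the Per-Protocol Cohort".
- **Who is Per-Protocol.** Section 11.3.3 takes randomized subjects who received their assigned treatment and "who complete their 6-week visit without any major protocol deviations".
- **Who is ITT.** Section 11.3.2: "All subjects who are randomized are included in the Safety/ITT Cohort". They are analyzed as randomized.
- **A conflicting rule.** Section 11.9: "All patients enrolled and randomized in the study will be included in all analyses".
- **Missing results.** Section 11.5 rules out imputation: "subjects missing results for a specific analysis will be excluded from that analyses".

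**The concern.** The study asks whether the device lowers opioid use without giving up pain relief (Sections 1 and 11.1). The WOMAC Pain test carries the second half of that question, and it is the only secondary endpoint for which 11.2.2 states when the objective is met. Yet it is the only one that 11.3.5 does not repeat in the randomized groups.

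A Per-Protocol analysis is an accepted part of a non-inferiority assessment. The weakness lies in using it alone. Each cohort can mislead in its own way: ITT by diluting a real difference through deviations, Per-Protocol by selecting on what happened after randomization. Agreement between the two is what makes the claim credible. Under 11.3.5, a subject who attends week 6 and gives a WOMAC score but had a major deviation or received the wrong treatment has no influence on the formal result. If such exclusions were related to pain and differed between the arms, the comparison would be biased.

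**Working it through.** **1. The passages side by side**

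| Analysis | Cohort rule | Formal success rule |
|---|---|---|
| Primary, daily morphine equivalent | Per-Protocol (11.3.4) | Yes, superiority |
| WOMAC Pain non-inferiority | Per-Protocol (11.3.5) | Yes, margin 11 |
| All other secondary endpoints | Safety/ITT and Per-Protocol (11.3.5) | None in 11.2.2 |
| All analyses | All randomized (11.9) | n/a |

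The last row cannot hold together with the first two.

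**2. The plan's own sample size**

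Inputs from 11.10: margin 11, SD 22, expected difference 0, one-sided 0.025, power 0.80.

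n per group = 2 × (1.960 + 0.842)² × 22² / 11² = 62.8, so 63 by the normal approximation. The noncentral t calculation gives 64 (power 0.801). The stated 64 is reproduced.

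**3. Is there room for an ITT run?**

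The plan randomizes 75 per group and allows for 10% loss: 75 × 0.9 = 67.5, taken as 67. Power of the same test by noncentral t is 0.860 at 75, 0.819 at 67 and 0.801 at 64 per group. Sample size is no reason to leave the ITT test out.

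**4. Illustration of selection**

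The inputs here are assumed, not taken from the protocol. Let a fraction f of active subjects be excluded although they have scores. Let their mean change be X points worse than that of the active subjects kept, and let sham exclusions be unrelated to pain. The Per-Protocol difference then looks better than the all-randomized difference by b = f × X.

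- SE = 22 × √(2/67) = 3.80
- With a true all-randomized difference of 11, P(false non-inferiority) = Φ(b/3.80 − 1.96)
- f = 10%, X = 22: b = 2.2, giving Φ(−1.38) = 0.084 (noncentral t 0.083)
- f = 10%, X = 44: b = 4.4, giving Φ(−0.80) = 0.21 (noncentral t 0.209)
- b = 0: 0.025

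For X from 11 to 44 points, noncentral t gives:

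| f | False non-inferiority |
|---|---|
| 5% | 0.035 to 0.083 |
| 10% | 0.047 to 0.209 |
| 15% | 0.063 to 0.407 |

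**5. Other directions**

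If exclusions are equally common and equally pain-related in both arms, the shifts cancel and the rate stays at 0.025. If the pain-related exclusions fall in the sham arm only, the sign reverses: Φ(−2.2/3.80 − 1.96) = Φ(−2.54) = 0.006. The Per-Protocol test is then conservative. Nothing in the protocol says which case applies.

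**The case against.** A reader might infer that subjects with a bad recovery are removed from the pain claim and that nothing checks it in the randomized groups. The documents do not support that reading, for these reasons:

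- Section 11.9 puts all randomized patients in all analyses. This contradicts 11.3.5 and does not cure it, but it means the exclusion is not settled. Section 11.9 also leaves room for sensitivity analyses, without committing to any.
- Section 11.2.2 lists the WOMAC scores, Pain included, among the additional secondary endpoints, with between-group t-tests and confidence intervals at each visit. With 11.3.5, this arguably gives an ITT comparison of WOMAC Pain. That comparison has no margin and does not decide the objective.
- The link from poor recovery to exclusion is thin. Major deviations are not defined. The restrictive requirements in 10.6 concern the operation and its anesthesia, which precede recovery, and postoperative analgesia is only recorded. The need for prohibited treatment appears in 10.10 as a reason for withdrawal.
- Subjects who withdraw or miss week 6 have no score, and 11.5 drops them from any cohort. The 10% allowance in 11.10 covers withdrawal and unavailable data, so it does not support the 10% in the illustration. Subject and treating investigator are blinded, which also argues against one-sided exclusion.
- The contrast holds only among secondary endpoints, since 11.3.4 also uses Per-Protocol for the primary: "Total Daily Morphine Equivalent, will be made using the Per-Protocol Cohort". Section 11.3.4 ties the required study objective to that endpoint, not to WOMAC Pain.

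All of this limits the size of the point. It does not explain why the one secondary test with a success rule should lack a run in the randomized groups.

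**Conclusion.** The point holds in a limited form. Section 11.3.5 decides the similar-pain-relief objective in a cohort defined by post-randomization events, without the same test in Safety/ITT, and it conflicts with 11.9. The subjects affected are those with a week-6 WOMAC score who had a major deviation or received the wrong treatment. Their number is unknown, and so are the size and direction of any bias. The 8% and 21% rates show only what an assumed one-arm, pain-related exclusion of 10% would do. They are not evidence that it will happen. The change should be made because it costs little and gives the non-inferiority claim a check in the randomized groups.

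**What to change.** Amend 11.3.5 so that the same WOMAC Pain non-inferiority test (margin 11, one-sided 0.025) is run in two cohorts:

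- the Safety/ITT Cohort, as randomized, using every available week-6 WOMAC score whatever the deviations;
- the Per-Protocol Cohort.

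The conclusion of similar pain relief should require consistent results in both, most simply significance in each. Since both must succeed, no alpha adjustment is needed. Reword 11.9 or 11.3.5 so that they name the same analysis sets. The same conflict exists between 11.9 and 11.3.4 and should be resolved in the same edit, but changing 11.3.4 alone would leave this test as it is.

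The cost is a sentence or two and one more run of a planned test, with no extra subjects. Requiring both results slightly lowers the chance of declaring non-inferiority. The change does not bring back subjects without a week-6 score, who remain excluded under 11.5.

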# 11.4 Statistical Methods

## 11.4.1 General

Categorical data will be summarized using frequency tables, presenting the subject counts and relative percentages. McNemar's chi-square may be used to assess within-subject changes in a bivariate response variable.

Continuous variables will be summarized by the mean, standard deviation, median, minimum and maximum. Within-subject changes will be analyzed parametrically using the paired t-test if the differences are normally distributed, or non-parametrically using the sign-rank test if the differences are not normally distributed.

The SAS system or equivalent statistical package will be used to perform all analyses.

Exact confidence intervals will be generated for estimates of proportions. Asymptotic confidence intervals will be generated for estimates of means. Except where otherwise noted, the p-values of all tests will be reported without any correction for the multiplicity of tests performed.

# 11.4.2 Derived Data – Change from Baseline Parameters

Within-subject change-from-baseline (pre-treatment baseline) values for a parameter are calculated as:

Change-from-Baseline = Follow-Up value – Pre-Treatment value

such that a positive value indicates an increase from the pre-treatment value to the follow-up value, whereas a negative result indicates the opposite.

#### 11.5 **Handling of Dropouts or Missing Data**

All endpoints will be analyzed "as-is" without any special data imputation methods used to replace missing data. Consequently, subjects missing results for a specific analysis will be excluded from that analyses.

#### **Poolability** 11.6

Data will be pooled from multiple study sites for this analysis. The justification for pooling is made on a clinical basis. The basis for pooling comes from three critical factors: the study sites must implement one common protocol; the sponsor must provide monitoring of study site compliance; the study sites must use common data collection procedures.

In addition, poolability across study sites will be assessed by presenting results across study centers and by analyzing treatment-by-site interaction using a two-way analysis of variance with Treatment, Site, and Treatment-by-Site interaction as terms in the model. Assessment of treatment-by-site interaction will be assessed at a 0.15 level of significance. A non-significant interaction effect will support poolability of study sites. A significant treatment-by-site interaction, if deemed to be only quantitative in nature as opposed to qualitative (i.e., if only due to a difference in magnitude of treatment effect across sites as opposed to a difference in direction of treatment effect across sites) will not necessarily disqualify study sites from being pooled. Note that prior to assessing interaction sites with less than 5 subjects will be combined. To avoid the scenario that the data from the combined super-site dominate the trial conclusion, sites with less than 5 enrolled subjects be combined according to their geographical closeness, and once a super-site have five or more enrolled subjects, then the forming of this super-site will stop and the forming of a new super-site will start. Site by treatment interactions of a quantitative nature, (i.e., all sites show the treatment to be beneficial, but perhaps to a different degree by study site) will not be considered to be an impediment to pooling. Site by treatment interactions qualitative in nature (i.e., the vast majority of sites show the treatment to be beneficial, but one or more sites show the treatment to be detrimental) will require extensive evaluation of the sites with contrary results to attempt to determine what factors at those sites led to the result.

<sup>1 Meinert, C. (1986). Clinical Trials: Design, Conduct, and Analysis. Oxford University Press, New York.

<sup>2 Medical Devices Dispute Resolution Panel Meeting of September 6, 2001 (Panel Transcript)

Lastly, poolability between subjects younger than 65 years old and subjects that are 65 years or older will be assessed using the same methodology described above by replacing Site with Age in the analyses performed. Assessment of treatment-by-age interaction will be assessed at a 0.15 level of significance. A non-significant interaction effect will support poolability of subjects younger than 65 years old and subjects that are 65 years or older.

# 11.7 Subgroup Analysis

Analyses for the Primary Effectiveness endpoint and the Secondary Effectiveness endpoint will be repeated for subjects younger than 65 years old and for subjects that are 65 years or older.

## 11.8 Analysis Windows and Definitions

Follow-up visits through 6-weeks should adhere to a window of  $\pm 05$  days when identifying the analysis visit. The reported-as visit will be used to identify the analysis visit for all follow-up visits after the 6-week visit.

# 11.9 Sensitivity Analyses

No imputations for missing data will be made for the Primary and Secondary Effectiveness Endpoints. All patients enrolled and randomized in the study will be included in all analyses. Sensitivity analyses may be considered and will be described in the final Statistical Analysis Plan for the study. Nevertheless, the totality of the results will be used when evaluating overall Study Success.

# 11.10 Sample Size Justification

Ultimately, the objective of this study is two-fold:

- 1. Primary Effectiveness Endpoint: Show that, on average, the Active iovera° treated subjects used less opioids than the Sham iovera° subjects.
- 2. Secondary Effectiveness Endpoint: Show that, on average, the Active iovera° treated subjects had similar pain relief as the Sham iovera° subjects.

A feasibility study was conducted to evaluate the safety and effectiveness of iovera°. In that study, the average (standard deviation) Total Daily Morphine Equivalent was 1826 mg (870 mg) among the iovera° subjects, and 2800 mg (1092 mg) among the non-iovera° subjects. All subjects were followed for 12 weeks. Assuming the following for the Primary Effectiveness Endpoint:

Statistical Hypothesis:  $H_0$ :  $\mu_{Active} \ge \mu_{Sham}$  vs  $H_1$ :  $\mu_{Active} < \mu_{Sham}$ ,

where  $\mu_{Active}$  is the average Total Daily Morphine Equivalent for the Active Treatment group, and  $\mu_{Sham}$  is the average Total Daily

Morphine Equivalent for the Sham Treatment group.

Statistical Test: two independent sample t-test

Statistical Significance: one-sided  $\alpha = 0.025$ 

Statistical Power:  $1 - \beta = 0.80$ 

Minimum Treatment Effect:  $\mu_{Active}$  -  $\mu_{Sham}$  = -7.14 mg

Common SD:  $\sigma = 13.1 \text{ mg}$ 

Minimum Sample Size: n = 54 per treatment group

It is expected that, on average, the Active treatment group will use 7.14 mg less opioids per day after 6-weeks of follow-up than the Sham treatment group. Assuming a common standard deviation of 13.1 mg for the Total Daily Morphine Equivalent and  $1 - \beta = 0.80$  statistical power, the two independent sample t-test will be statistically significant at a one-sided  $\alpha = 0.025$  level of statistical significance when there are a minimum of 54 analyzable subjects in the Active treatment group and 54 analyzable subjects in the Sham treatment group.

The study is also powered to show that, on average, the pain relief among Active subjects is not worse than the pain relief among the Sham subjects. The non-inferiority margin, Δ, represents how much worse the pain relief among the Active subjects can be than among the Sham subjects, and still be considered "not worse than" the Sham pain relief. In Escobar, et al. the Minimum Detectable Change (MDC95) for WOMAC Pain was calculated as 22.39. Standard deviations for the Change in WOMAC Pain in that paper ranged from 18 to 22, depending on the cohort. In the feasibility study, pain was assessed using the Knee injury and Osteoarthritis Outcome Score (KOOS) instrument. In that study, the average (standard deviation) Change in KOOS Pain at 6-weeks was -24.0 (13.5) among the iovera° subjects, and -18.3 (27.7) among the non-iovera° subjects. In this study, the non-inferiority margin is set at 11, a value roughly one-half the MDC95 quoted in Escobar, and that is also equal to roughly one-half of the estimated standard deviation of 22 for the Change from Baseline WOMAC Pain results. That is:

Non-Inferiority Margin ( $\Delta$ ) = 11

 $\simeq$  Escobar MDC95 / 2 = 22.39 / 2

 $\simeq$  Change from Baseline WOMAC Pain SD / 2 = 22 / 2

Assuming the following for the Major Secondary Effectiveness Endpoint:

Statistical Hypothesis:  $H_0$ :  $\mu_{Active} > \mu_{Sham} + \Delta \text{ vs } H_1$ :  $\mu_{Active} < \mu_{Sham} + \Delta$ ,

where  $\mu_{Active}$  is the average Change from Baseline in WOMAC Pain for the Active Treatment group,  $\mu_{Sham}$  is the average Change from Baseline in WOMAC Pain for the Sham Treatment group, and  $\Delta$  is

the non-inferiority margin.

Statistical Test: two independent sample t-test

Statistical Significance: one-sided  $\alpha = 0.025$ 

Statistical Power:  $1 - \beta = 0.80$ 

Expected Difference:  $\mu_{Active} - \mu_{Sham} = 0$ 

Common SD:  $\sigma = 22$ 

Non-Inferiority Margin:  $\Delta = 22 / 2 = 11$ 

Minimum Sample Size: n = 64 per treatment group

Proprietary & Confidential

<sup>3 Escobar A, Quintana JM, Bilbao A, Aróstegui I, Lafuente I, Vidaurreta I. Responsiveness and clinically important differences for the WOMAC and SF-36 after total knee replacement. Osteoarthritis Cartilage. 2007 Mar; 15(3):273-80.

It is expected that, on average, the Active treatment group will have the same pain relief after 6-weeks of follow-up as the Sham treatment group. Assuming a common standard deviation of 22 for the Change from Baseline WOMAC Pain, a non-inferiority margin of 11, and  $1 - \beta = 0.80$  statistical power, the two independent sample t-test will be statistically significant at a one-sided  $\alpha = 0.025$  level of statistical significance when there are a minimum of 64 analyzable subjects in the Active treatment group and 64 analyzable subjects in the Sham treatment group.

Lastly, the study is powered to evaluate Length of Stay, the number of days from surgery to discharge. Assuming a common standard deviation of 1 day for Length of Stay and  $1 - \beta = 0.80$  statistical power, the Wilcoxon rank-sum test will be statistically significant at a one-sided  $\alpha = 0.025$  level of statistical significance when there are a minimum of 69 analyzable subjects in the Active treatment group and 69 analyzable subjects in the Sham treatment group.

To account for up to 10% of the subjects withdrawing early or not having data available for the analysis of the primary effectiveness endpoint, a total of 150 subjects (Randomized 1:1 to approximate 75 Active treatment subjects plus 75 Sham treatment subjects) will be randomized and treated.

#### 12. ADVERSE EVENTS

The study Investigator and Coordinator will evaluate, characterize and record in the eCRF all adverse events (AEs) occurring in all subjects from the initiation of study treatment to study exit (or premature withdrawal). Device or procedure related AEs will be followed until resolution. AEs may be reported spontaneously by the subject or detected by the Investigator or coordinator. AEs should be evaluated for diagnoses not just symptoms (i.e., "angina", not "chest pain").

AEs may be either spontaneously reported or elicited during questioning and examination of a subject. All AEs must be completely recorded within the Subject's source documentation. All AEs will be evaluated by the Investigator for relationship to the ioverao device and to the treatment.

In addition to verbatim terms, the Sponsor will categorize all AEs using MedDRA preferred terms (PT) and system organ classes (SOC). Analysis will report both verbatim and MedDRA terms.

Adverse events (AEs) will be assessed continuously from the initiation of study treatment through study exit. Per ISO14155:2011, an AE is any untoward medical occurrence, unintended disease or injury, or untoward clinical signs in subjects, users or other persons, whether or not related to the investigational medical device. An AE can arise from any use of the device (e.g., off-label use, use in combination with any drug) and from any route of administration.

Timely and complete reporting of all AEs assists the Sponsor in identifying any untoward medical occurrence, thereby allowing:

- 1) protection of the safety of study subjects;
- 2) a greater understanding of the overall safety profile of the device;
- 3) recognition of device-related ill effects;
- 4) appropriate modification of study protocols;

-

<sup>4 Definition from ISO14155:2011

- 5) improvements in study design or procedures; and
- 6) adherence to worldwide regulatory requirements.

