#### 10.9 **Study Exit**

When the final study visit is complete, the Subject's participation in the study is complete and the Investigator, or designee, will complete the study exit eCRF.

If a Subject is experiencing an unresolved device or iovera° treatment related adverse events at the final study visit, the Subject will be followed by the Investigator until resolution occurs

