# **10.10** Subject Discontinuation

A Subject may be withdrawn from the study prior to completion for any of the following reasons:

- Voluntary withdrawal of consent
- Adverse event preventing continued study participation
- Investigator believes risk of further subject participation outweighs benefit
- Medical need for prohibited medications or treatment
- Persistent non-compliance or lost to follow-up (A Subject is considered lost to followup after the site makes 3 attempts to contact the via email or phone call and a certified letter is sent to the Subject.)

The Investigator/Coordinator will complete a study exit form in the eCRF for any subject who prematurely discontinues from the study. If discontinuation was the result of an AE, the AE will also be recorded in the eCRF

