#### 11. STATISTICAL METHODOLOGY AND ANALYSES

#### 11.1 Introduction

This is a prospective, randomized, sham-controlled, multi-center, post-market trial to evaluate the iovera° device in treating pain associated with total knee arthroplasty (TKA). The study is designed to investigate whether iovera° treatment prior to TKA decreases cumulative patient opioid use over the course of 6 weeks following TKA while maintaining similar levels of pain relief.

The study will also investigate whether there is a relationship between patients treated with iovera° and length of hospital stay; patient reported pain and function as measured by WOMAC; patient satisfaction; and improved physical rehabilitation as measured by functional performance measures and range of motion.

The primary safety endpoint is the onset of device-related adverse events through twelve-weeks after TKA surgery. The primary measure of effectiveness is the Total Daily Morphine Equivalent (TME) of pain medications used from Day of Discharge to the 6-week follow-up visit. In addition. Change from Baseline in WOMAC Pain at the 6-week follow-up visit will be evaluated as a secondary endpoint. A variety of secondary effectiveness endpoints, including performance and pain assessments, will be measured.

Up to 8 study sites within the United States will screen a sufficient number of subjects to ensure that 150 subjects (Randomized 1:1 to approximate 75 Active Treatment subjects plus 75 Sham Treatment subjects) will be randomized and treated.

Subjects will be randomized either to receive therapeutic treatment with the iovera° treatment or to receive a sham treatment with the iovera° treatment, using a balanced 1:1 active-to-sham randomization stratified by Study Site.

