# 11.2.3 Safety

The frequency of each adverse event will be summarized by seriousness, severity and by relationship to the device. Since some subjects may report the same event several times (e.g., headache), the first occurrence of the worst reported case of the event will be used for the purpose of analysis. Refer to the User Guide for full list of expected adverse events.

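### Adverse event recording stops at premature withdrawal, so device-related events that begin after an early exit but within the 12-week primary safety window are not captured

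*Protocol*

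**What the plan says.** Section 11.1: "The primary safety endpoint is the onset of device-related adverse events through twelve-weeks after TKA surgery".

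Section 12 sets the recording period. Staff record AEs "occurring in all subjects from the initiation of study treatment to study exit (or premature withdrawal"). The next sentence adds "Device or procedure related AEs will be followed until resolution", without limiting this to subjects who complete the study.

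Section 10.10 lists the grounds for early discontinuation. Withdrawal of consent is one. The others include an AE, the investigator's judgement of risk and benefit, need for a disallowed therapy, non-compliance and loss to follow-up. The site then completes an exit form, and "If discontinuation was the result of an AE, the AE will also be recorded in the eCRF".

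Section 10.9 covers the end of participation: for unresolved device- or treatment-related "adverse events at the final study visit, the Subject will be followed by the Investigator until resolution occurs". Section 10.7.2 sends the reader to section 10.8 for this rule, but 10.8 deals with photographs.

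On analysis, section 11.3.2 states "All subjects who are randomized are included in the Safety/ITT Cohort", and section 11.2.3 says that where a subject reports an event repeatedly, "the first occurrence of the worst reported case of the event will be used for the purpose of analysis".

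The follow-up visits in section 10.7 fall at weeks 2, 4, 6 and 12, all counted from surgery.

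**The concern.** The endpoint has a fixed window, and the recording rule can close earlier. The study treatment is given once, before surgery, and leaving the study does not undo it. A subject who leaves at week 2 remains exposed to whatever the treatment may still cause, but nobody is asked to record it. Several grounds for exit in section 10.10 do not imply that the subject refuses further contact, so the information is given up by rule and not by necessity.

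At stake is the completeness of the primary safety endpoint. A missed event is counted as no event, so the gap works in the device's favour.

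A related gap concerns subjects who are treated and then do not have the TKA. Visits and safety window are both counted from an operation that did not take place.

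**Working it through.** The protocol states no figure that can be reproduced here. The check is to follow each kind of subject through the rules.

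**1. Subject who leaves because of a device-related AE.** The event starts before exit, so it lies inside the section 12 recording period. Section 10.10 requires it in the eCRF. The endpoint counts onset, and the subject stays in the Safety/ITT Cohort. The event is counted.

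**2. Subject who leaves early, for any reason, and has a new device-related AE before week 12.** Onset is inside the section 11.1 window but after recording has stopped under section 12. The subject remains in the denominator. The event is not counted. The same holds for a subject of type 1 who later has a different device-related event, because section 11.2.3 tabulates each event.

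**3. Subject whose recorded AE worsens after exit.** Section 11.2.3 uses the worst reported case. Section 12's follow-to-resolution sentence may bring the worsening to light for a device- or procedure-related event. The recording period has ended, however, and section 10.10 does not ask for an update, so it is unclear whether the worse grade enters the data.

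**4. Subject treated, no TKA.** Section 10.5 places treatment 0 to 7 days before surgery, and section 10.6 still has the site confirm that surgery can safely go ahead. If it does not, no visit is scheduled after Visit 2, and the 12 weeks have no starting point.

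**Direction of the error.** For one arm let

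- N = subjects randomized,
- D = subjects with a recorded device-related AE,
- M = subjects with no recorded device-related AE whose first one begins after early exit and by week 12.

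Recorded crude rate = D / N. Rate over the full window = (D + M) / N. Shortfall = M / N, which is zero or positive. The recorded rate can be too low but, for this reason, never too high. The same holds row by row for single AE terms. The error in the difference between arms is M/N on active minus M/N on sham, whose sign the protocol does not fix.

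**Length of window lost, as illustration only.** Exit at week 2: (12 − 2) / 12 = 83% of the post-operative window. Exit at week 6: (12 − 6) / 12 = 50%. The exit times are assumed. The protocol gives neither their distribution nor a rate of late-onset device events, so M cannot be estimated.

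**The case against.** The strongest case against is that the protocol already protects what matters most, and much of it stands.

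- A reader might infer that subjects who leave because of a device event vanish from the primary safety endpoint. The documents contradict this: the event is recorded under section 10.10, counts by onset under section 11.1, and the subject stays in the cohort under section 11.3.2.
- A reader might see a contradiction between section 10.9, triggered by "If a Subject is experiencing an unresolved device or iovera° treatment related adverse events at the final study visit", and section 12. Section 10.9 does not restrict follow-up to that case, and section 12's sentence is general. This is a rule with a narrower restatement. The weakness is practical: a site working from section 10.10 would not find the general rule there.
- A reader might take the 10% allowance in section 11.10, 10% × 150 = 15 subjects, as the number affected. It is not a bound. It covers early withdrawal together with missing data for the primary effectiveness endpoint, which is measured at 6 weeks. It is neither a rate of exit before week 12 nor a rate of device-related exit.
- The two to three months in section 1 is a duration of effect, not a time to onset of AEs, and section 9.4 lists risks without timing. Nothing in the protocol shows that late-onset device events are common, or that exits would differ by arm.
- Telephone contact adds little for subjects already lost after three attempts and a certified letter, and nothing for those who withdraw consent.
- Subjects without TKA should be few, since treatment comes within a week of a scheduled operation. They are also told to report AEs between visits.

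These points limit the size of the problem. They do not close the gap between a 12-week endpoint and a recording rule that may end sooner, nor supply a safety schedule for a treated subject without TKA.

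**Conclusion.** The point holds as an incomplete capture rule: the recording period in section 12 can be shorter than the window of the primary safety endpoint. The loss is confined to device-related AEs that begin or worsen after an early exit and before week 12. With early leavers kept in the denominator, the crude rate can only be understated.

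This rests on two assumptions. First, the rate is a simple proportion of the Safety/ITT Cohort; sections 11.3.2 and 11.9 point that way, and an analysis that allowed for time observed would behave differently. Second, some early leavers have not withdrawn consent and can be reached, which the grounds in section 10.10 allow.

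The size cannot be derived from the protocol and may be small. The gap for treated subjects without TKA is real but of unknown frequency. The wrong cross-reference in section 10.7.2 is editorial. Together these justify an inexpensive amendment. They do not show that the safety endpoint is unusable.

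**What to change.** - **Sections 12 and 10.10:** end AE collection at 12 weeks after TKA for every treated subject who has not withdrawn consent, by telephone where visits have stopped. For subjects who do not have TKA, state an equivalent period counted from study treatment.
- **Section 10.9:** align with section 12 so that follow-up of device- or treatment-related AEs to resolution expressly includes early exits, and refer to it from 10.10.
- **Section 10.7.2:** change the cross-reference from 10.8 to 10.9.

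The cost is a short amendment and a few telephone contacts per affected subject. The number of such subjects is not known from the protocol but should be small. Some contacts will fail, and events reported by telephone will be less well documented than those seen at a visit. Neither is a reason to stop asking.
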